10.8 Exploratory Objectives

- To monitor safety issues, recording serious adverse events in both groups
- Quantify cytokine levels to further understand the inflammatory processes involved

10.9 Exploratory Endpoints

- Frequency and type of SAEs
- Analyze cytokine blood levels

10.10 Clinical Endpoints

The following clinical endpoints will be assessed:

- ICU length of stay
- Survival status at ICU discharge (dead or alive)
- Survival status at hospital discharge (dead or alive)
- Duration of mechanical ventilation
- Survival status at disconnection from mechanical ventilation (dead or alive)
- Ventilator free days to day 28 (an ordinal scale composed of survival to hospital discharge and days alive and free of ventilation where death in the hospital is assigned a score of – 1)

10.11 Proposed Type of Analyses

For the feasibility objectives of this pilot RCT we will present point estimates as proportions with 95% confidence intervals. We will present continuous data as means (standard deviations), or medians (interquartile ranges), as appropriate.

With respect to patient accrual, our goal is to enrol 72 patients across Canadian sites for the pilot study given a period of one year of active enrolment per site. Failure to do so will prompt us to modify our plans for a future trial. If our accrual is as anticipated, or better, we will not modify the eligibility criteria. If our accrual rate is marginal (that is, barely achieves our goals), we will examine the number of patients excluded on the basis of each exclusion criterion and reconsider the necessity for any criterion that has resulted in a large number of excluded patients.

10.12 Proposed Frequency of Analyses

Due to the small size and short duration of this pilot RCT, we have not planned for any domain-specific interim analyses. We have planned, however, to provide the Data Safety and Monitoring Board (DSMB) with analyses by group at the completion of this pilot RCT. Further details regarding DSMB commitment will be detailed in the DSMB charter. These analyses will include relative use of neuromuscular blockade, sedative infusions, and vasopressor infusions; and relative rates of prone positioning, ECMO, and mortality. In this pilot RCT, we will not undertake any formal statistical inference or testing and will report descriptive statistics as required. We

will also consider controlling for centre and providing both unadjusted analyses and analyses adjusted for age and baseline oxygenation, and duration of ventilation prior to enrolment using Bayesian (generalized) linear models. The results from these models will be summarised using the posterior mean and 95% credible intervals. All these analyses will include all randomised patients adhering to the intention to treat principle. We will use complete case analyses, with the level of missingness reported for each outcome. Investigators will remain blinded to these clinical results, while the full ULTIMATE trial moves forward. Due to the pilot study design of the trial and its short duration, no subgroup analyses are planned.

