9 SAFETY AND REPORTING REQUIREMENTS

The critically ill patient population are admitted to the ICU for life-sustaining therapies (e.g. mechanical ventilation, vasopressors, renal replacement therapy). Many of the potential subjects will be admitted with the expectation of receiving end-of-life care and possibly dying in the ICU. Furthermore, medical complications are likely to occur in this population, consistent with the nature of their progressive illness (e.g. nosocomial infections; septic shock; multi-organ failure; need for vasopressors; acute renal failure and the need for renal replacement therapy; arrhythmias; cardiac arrest; coma; aspiration; venous thromboembolism). Due to these relatively unique morbidity and mortality expectations in the critically ill patient population and the intervention's safety profile, generic adverse events will not be collected for this study and only study-procedure related SAEs will be collected and reported (see section below). Expected events occurring in the course of life-support patient, and not related to study procedure, will not be reported as SAEs in the ULTIMATE trial.

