9.3 Procedures for Expedited Reporting

Responsibility for Reporting Serious Adverse Events to Sponsor

Ozmosis will be responsible for submitting SAE reports (Initial and/or Follow-up reports) received from the sites, to the Sponsor and the domain Principal Investigators within 1 business day after receipt of the SAE form at Ozmosis.

Reporting Serious Adverse Events to Data Safety Monitoring Board (DSMB)

Ozmosis will be responsible for submitting SAE reports received from the sites to the DSMB chair. The initial SAE report will be sent within 1 business day of receipt of the SAE form at Ozmosis, with follow-up reports and synthesis from Sponsor and Domain Principal Investigators being sent when available.

Reporting Serious Adverse Events to Local Research Ethics Boards

Investigators must follow their local Research Ethics Boards (REBs)/Institutional Review Boards (IRBs) guidelines for SAE reporting. Documentation of correspondence with REBs/IRBs should be forwarded to Ozmosis.

Documentation can be any of the following:

- letter from the REB/IRB acknowledging receipt
- stamp from the REB/IRB, signed and dated by REB/IRB chair, acknowledging receipt
- letter demonstrating the SAE was sent to the board

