10 STATISTICAL ANALYSES

10.1 Study Population

The number of patients planned to be randomized into this domain protocol is 72. This would allow for testing the validity of our eligibility criteria, ventilation protocols, and study procedures. It will also allow for an assessment of crossovers at numerous sites involving a number of clinicians. The sample size would allow for an assessment of feasibility objectives over a reasonable time period of 1 year as well as allow us to detect an adherence rate of 80% + 10% (meaning 80% + 10% of study patients will have fewer than 10% of monitored values as major deviations).

For the feasibility objectives of this pilot RCT we will present point estimates as proportions with 95% confidence intervals. We will present continuous data as means (standard deviations), or medians (interquartile ranges), as appropriate. We will not undertake formal statistical interference for any outcomes.

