10.15 Randomization Scheme

We will use web-based, allocation-concealed randomization, stratified by centre, accessible 24 hours per day. We will randomize patients 1:1 (experimental:control) using randomly variable, undisclosed block sizes. Research assistants and/or clinical respiratory therapists will screen all mechanically ventilated patients for eligibility on a daily basis.

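### As this protocol states it, the DSMB sees all-cause deaths by arm only once the pilot is complete, and no review during accrual or pause guidance is given or cited

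*Protocol*

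**What the plan says.** Section 10.12 gives small size and short duration as the reason that "we have not planned for any domain-specific interim analyses". It then plans "to provide the Data Safety and Monitoring Board (DSMB) with analyses by group at the completion of this pilot RCT", lists mortality among those analyses, and leaves further detail of the DSMB's commitment to a charter. The domain protocol states no event count, rate or difference that would prompt a hold on recruitment.

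The route to the DSMB during accrual is in section 9.3: "Ozmosis will be responsible for submitting SAE reports received from the sites to the DSMB chair", with the initial report due within 1 business day of receipt of the form. Section 9 limits what enters that route: "only study-procedure related SAEs will be collected and reported". Under section 9.1 the attending physician judges relatedness, and a possible contribution is enough. Section 9.4 ends reporting at ICU discharge or 30 days, whichever comes first.

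On size and duration, section 10.1 says "The number of patients planned to be randomized into this domain protocol is 72", and section 10.11 frames accrual as "given a period of one year of active enrolment per site".

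**The concern.** The two safety routes in this protocol leave a gap between them. The SAE route is fast, but it carries individual cases already judged to be linked to a procedure. The by-group analysis covers all deaths in both arms, but its stated time is the end of the pilot.

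Section 9 itself names septic shock, multi-organ failure and cardiac arrest among the complications expected in these patients, and says that expected events unrelated to the study procedure are not reported as SAEs. If ECMO raised mortality through such causes, each death could reasonably be put down to the illness. Only a count of all deaths by arm, with denominators, would show the excess. Control deaths would rarely be called procedure-related, so the SAE stream cannot supply that comparison.

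At stake is whether later patients are randomised to an invasive intervention while data that could show a large excess lie untabulated. ICU and hospital survival are already recorded (sections 6.1 and 10.10), so the tables need no new data.

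**Working it through.** **The plan's own figure.** The only quantitative basis for 72 is in section 10.1, the ability to "detect an adherence rate of 80% + 10" per cent. Reading this as plus or minus 10 points, the 95% half-width is 1.96 × √(0.8 × 0.2 / 72) = 0.092, or 9.2 points. This agrees with the stated precision and is not disputed. It concerns adherence, not mortality.

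**Are there enough deaths to tabulate?** Inputs: 72 patients (10.1), 1:1 allocation (10.15), so about 36 per arm, and ARDS mortality of 34–65% (3.1).

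- Per arm with no treatment effect: 36 × 0.34 = 12.2 to 36 × 0.65 = 23.4.
- In total: 72 × 0.34 = 24.5 to 72 × 0.65 = 46.8.
- Extra deaths in the ECMO arm for a true excess of 10, 20 or 30 points: 36 × 0.10 = 3.6, 36 × 0.20 = 7.2, 36 × 0.30 = 10.8.

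**Is the duration short?** The one-year clock runs per site. If sites open at different times, calendar time from first to last patient can exceed a year.

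**What could looks during accrual detect?** This is an illustration. The documents give no look schedule, prior, threshold or assumed excess.

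- Looks after 24 and 48 patients, taken as 12 and 24 per arm.
- Deaths in each arm binomial; flat Beta(1,1) priors, so the posterior after x deaths in n is Beta(1 + x, 1 + n − x).
- Flag at a look if P(ECMO mortality > control mortality) ≥ 0.95.
- Chance of at least one flag = P(flag at first look) + P(no flag at first, flag at second), by exact enumeration of all death counts.
- Delay variant: the last 6 patients per arm have no outcome yet at each look, leaving 6 and 18 per arm.

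| Control | ECMO | All outcomes known | Last 6 per arm pending |
|---|---|---|---|
| 40% | 40% | 0.079 | 0.074 |
| 40% | 50% | 0.221 | 0.177 |
| 40% | 60% | 0.460 | 0.353 |
| 40% | 70% | 0.728 | 0.597 |

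The 40% is an assumption within the 34–65% range. At the ends of the range, with all outcomes known, the no-difference rate is 0.080 at both 34% and 65%. A 20-point excess is flagged with probability 0.463 (34% v 54%) and 0.540 (65% v 85%).

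As a concrete case at the second look, 14/24 ECMO deaths against 8/24 control deaths gives a posterior probability of 0.956, which flags; 13/24 against 8/24 gives 0.923, which does not.

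A flag at the first or second look would come with 72 − 24 = 48 or 72 − 48 = 24 patients not yet randomised.

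**The case against.** The strongest reply is that this is a domain within a platform. Section 10.12 rules out only domain-specific interim analyses and defers DSMB detail to a charter; the master protocol is cited throughout but is not at hand. Meeting frequency, closed tables and pause guidance often sit in those documents. This stands, and it limits the point to what this protocol states. A reader might infer that no mortality excess could pause the pilot, that the chance of an early by-arm review is nil, or that the charter would have to override section 10.12. The text supports none of these: planning a report at completion does not forbid an earlier one.

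Next, the SAE route is real protection. Relatedness includes possible contribution, reports reach the DSMB chair quickly, and sponsor and investigator synthesis follows when available. The initial report includes ventilation type and dates (9.2), so the arm can probably be inferred. A reader might infer that device deaths or massive haemorrhage go unseen until the end. They do not, if recognised as related. What remains is deaths not attributed to a procedure, and the lack of denominators.

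Third, early looks are weak. A 10-point excess is flagged only about 22% of the time, and pending outcomes cut the 20-point figure from 0.46 to 0.35. Variable blocks within centres do not guarantee equal arms, and a pause spares patients only if the DSMB then stops recruitment. All of this stands. It argues against expecting much for small effects, not against tabulating deaths.

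Last, a reader might infer that a harm-only look leaves later efficacy analysis untouched. That is too strong. Section 4.2 allows pilot patients to roll into the definitive trial, whose primary question is hospital mortality (4.1). Looking only for harm does not inflate false claims of benefit, but stopping early for harm can reduce power and bias the estimate.

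**Conclusion.** The point holds in limited form. As stated in this protocol, all-cause mortality by arm goes to the DSMB at completion, and no interim review or pause guidance is given for this domain. The SAE stream does not replace it for deaths not attributed to a procedure, or for deaths after ICU discharge or day 30. Whether the gap exists in practice depends on the charter and master protocol.

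The stated reason, small size and short duration, has force against formal efficacy testing but little against a descriptive harm review with about 24 to 47 expected deaths. That range assumes the background ARDS mortality in section 3.1 applies to this selected population, which excludes patients over 65. The flag probabilities show that a large excess could often be seen before the last patient and a small one usually could not. They rest on the assumed looks, priors, threshold and control mortality, and are not a recommended rule.

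**What to change.** In section 10.12, state that the existing DSMB also receives closed tables of all-cause deaths and of procedure-related SAEs by arm, with denominators, at set points during accrual, for example after about one third and two thirds of patients. Name one mortality endpoint for these tables and report how many patients have no outcome yet. Keep investigators blinded to the by-arm results, as section 10.12 already intends. If the platform or the charter already provides for this, cite the rule and reconcile it with the timing in section 10.12. The sponsor and the DSMB should set any criterion that prompts a pause for review, say where it is written, and report its operating characteristics with outcome delay included.

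The cost is one paragraph and two extra closed tables from data already collected. There is a small chance of an unnecessary review pause (about 8% under the illustrative looks). If recruitment stopped early for harm, there would be some effect on power and estimation in the definitive trial, which its analysis plan should acknowledge.

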10.13 Feasibility Outcomes

- 1) Adherence to our explicit ventilation protocols will be adequate if more than 80% of patients have fewer than 10% of monitored values as major protocol deviations.
- 2) The number of protocol withdrawals or off-protocol treatment with VV-ECMO will be acceptable if fewer than 10% of patients cross over, when not allowed by protocol.
- 3) Patient accrual will be adequate if we recruit at least 60 patients over 1 year of active site enrolment.

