6 STUDY PLAN

6.1 Study Schedule

Consenting eligible patients will be randomized to either the experimental group or the control group. Patients randomized to the experimental group will receive ultra-protective ventilation using ECMO. Patients requiring ventilation for longer periods may continue ventilation via ECMO or receive Conventional Lung-Protective Ventilation (LPV), as deemed necessary by the treating physician. Patients randomized to the control group will receive LPV. If the patient’s clinical status declines and meets the ECMO criteria for ventilation (as established by prior randomized clinical trials), they would be eligible to receive ECMO if their treating physician deems that appropriate. Please see sections 7.2 and 7.4 below.

Study procedures common to both groups will continue for the duration of the ICU stay up to day 30. We will collect daily data during mechanical ventilation until day 30. Thereafter, we will follow patients to the time of hospital discharge and record ICU/hospital survival. We will also assess health-related quality of life by telephone interview or via email 6 months after randomization.

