8.1.2 Maintenance and Weaning of Ultra-Protective Ventilation

Deep sedation, paralysis, and these low-intensity mechanical ventilation settings will be maintained for at least 48 hours after ECMO initiation. The clinical team will make adjustments to the VV-ECMO settings to maintain the same PaCO₂, pH and PaO₂ and SpO₂ targets as above. These adjustments to VV-ECMO sweep gas or blood flow will be dictated by ABG results drawn as clinically indicated.

On study day 3, patients will then enter the maintenance and weaning phase – neuromuscular blockade will be discontinued, and lighter sedation levels (SAS 2-3) will be targeted unless otherwise decided by the attending physician.

During the first 7 days after randomization and once neuromuscular blockade is stopped and patients are making spontaneous breathing efforts, we will use sweep gas flow (primary) and sedation (secondary) to modulate spontaneous efforts to maintain low intensity ventilation, targeting the estimated dynamic trans-pulmonary driving pressure (ΔP_{L-dyn}) and tidal volume.

Clinicians will measure patient respiratory effort by calculating ΔP_{occ} (which is always zero or negative):[26]

- Perform expiratory hold and record trough pressure with next effort (record as = PEEP if no efforts made)
- Calculate $\Delta P_{occ} = \text{trough pressure} - \text{PEEP}$
- Calculate $\Delta P_{L-dyn} = (\text{Peak airway pressure} - \text{PEEP}) - 0.67 \times \Delta P_{occ}$

To maintain $\Delta P_{L-dyn} \leq 23$ cm H₂O while maintaining a V_T of 8 ml/kg PBW or lower, the treating team will adjust in the following order: a) the mechanical ventilator, b) the sweep gas flow, and c) sedation levels. After day 7 driving pressure and V_T targets, as well as sweep gas settings will be determined by the attending physician.

We will wean ECMO prior to liberating from mechanical ventilation and provide explicit protocols for weaning ECMO (See Manual of Procedures). Briefly, patients will be assessed daily for ability to discontinue ECMO – all patients who are not paralyzed and are breathing spontaneously on sweep gas flow of 4 L/min or less, and who are receiving an FiO₂ of ≤ 0.6 on the mechanical ventilator with a PaO₂/FiO₂ > 150 will undergo a trial of sweep gas off on ECMO. ECMO will be discontinued if patients tolerate sweep gas off for at least 12 hours (i.e., no significant hypoxemia, respiratory acidosis, or work of breathing).

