8.2 Control Group: Conventional Lung-Protective Ventilation (LPV)

Patients randomized to the control group will be treated with the same explicit standard ventilation protocol that we used to good effect in several recent multi-centre trials in ARDS. The overall goals for this strategy are to minimize volutrauma and atelectrauma to the extent possible with standard of care ventilation.

Volume Assist Control will be the default mode and will be set to achieve lower tidal volumes (6ml/kg PBW) and plateau pressures ($P_{PLAT} \leq 30$ cm H₂O). Other modes may also be used at the discretion of the attending physician. The same limits to P_{PLAT} and V_T apply regardless of ventilator mode. Only when the patient is being ventilated with Pressure Support of 10 cm H₂O support or less and with PEEP ≤ 8 cm H₂O and FiO₂ ≤ 0.4 will these thresholds (P_{PLAT} and V_T) no longer apply. We recommend that PEEP and FiO₂ be adjusted according to oxygenation targets using the higher PEEP-FiO₂ table, allowing for use of lower PEEP if clinically indicated. If the plateau pressure target is exceeded, V_T will be reduced as needed to a minimum of 4 ml/kg PBW, and/or PEEP reduced and FiO₂ increased as necessary to achieve $P_{PLAT} \leq 30$ cm H₂O while providing adequate oxygenation.

If a patient's state worsens and meets entry criteria from the EOLIA trial (persistence of either $\text{PaO}_2/\text{FiO}_2 < 80$ or $\text{pH} < 7.15$ and $\text{PaCO}_2 > 60$) they can receive VV-ECMO (a secondary outcome) at the discretion of the attending physician.

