10.7 Secondary Endpoints

- Evaluate number of protocol deviations and their causes (control group: $V_T > 8 \text{ ml/kg}$, $P_{PLAT} > 30 \text{ cm H}_2\text{O}$; experimental group: $V_T > 8 \text{ ml/kg}$, $P_{PLAT} > 30 \text{ cm H}_2\text{O}$, $\Delta P_{L-dyn} > 23 \text{ cm H}_2\text{O}$) over 2 consecutive data points for a minimum of 48 hours.
- Classify crossovers as consistent with, or in deviation of, the study protocol and detailed documentation will be required for crossovers classified as deviations.

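### The adherence criterion applies fixed ventilation limits without excluding periods when the protocol has lifted them, so a patient who broke no limit in force can be scored non-adherent

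*Protocol*

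**What the plan says.** **The criterion.** Protocol section 10.13 judges adherence adequate if "more than 80% of patients have fewer than 10% of monitored values as major protocol deviations". It gives no period over which values are monitored.

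**The deviation limits.** Section 10.7 counts a deviation when tidal volume exceeds 8 ml/kg or plateau pressure exceeds 30 cm H₂O in either arm, or when dynamic transpulmonary driving pressure exceeds 23 cm H₂O in the experimental arm, "over 2 consecutive data points for a minimum of 48 hours". It names no end day and no exempt ventilator state.

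**The data.** Section 6.1: "We will collect daily data during mechanical ventilation until day 30". The footnotes to the schema in section 6.2 give the same day-30 horizon for both groups.

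**Where the limits are lifted.**
- Experimental arm, section 8.1.2: "After day 7 driving pressure and V_T targets, as well as sweep gas settings will be determined by the attending physician". The release goes by calendar day.
- Control arm, section 8.2: only on pressure support of 10 cm H₂O or less with PEEP of 8 or less and FiO₂ of 0.4 or less "will these thresholds (P_{PLAT} and V_T) no longer apply". The release goes by ventilator state, with no end day.

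**The concern.** The treatment sections switch off limits that the scoring sections go on applying. If sections 10.7 and 10.13 are followed to the letter, a value the protocol permits is counted as a deviation. Values recorded with no limit in force also enlarge the denominator and can mask breaches from the first week, when the experimental arm's ventilation is protocolised.

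Adherence is one of three feasibility criteria in section 10.13. Section 4.2 makes carrying pilot patients into the definitive trial depend on feasibility being shown. The trial is open-label, so a scoring window chosen after the ventilation data have been seen would leave the result open to choice.

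**Working it through.** **Inputs.** 72 patients (section 10.1). A patient passes with fewer than 10% of values deviating, and the trial passes with more than 80% of patients passing (section 10.13). Daily data run to day 30 (section 6.1). One value per day per patient is my assumption, because the protocol does not define a monitored value.

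**1. The plan's own figure.** Section 10.1 says the sample would "allow us to detect an adherence rate of 80% + 10" percent, which I read as plus or minus 10 points, with "point estimates as proportions with 95% confidence intervals". The 95% half-width at 80% is 1.96 × √(0.8 × 0.2 / 72) = 0.092, or 9.2 points. The stated precision holds. The problem lies in what is counted, not in the sample size.

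**2. A patient who broke no limit in force.**
- Experimental: 20 ventilated days, days 1–7 compliant, tidal volume above 8 ml/kg on 3 consecutive days after day 7. As written, 3/20 = 15%: non-adherent. Counting tidal-volume values only to day 7, 0/7: adherent.
- Control: 10 compliant days, then 3 days in the low-support state with tidal volume above 8 ml/kg. As written, 3/13 = 23%: non-adherent. Outside the exempt state, 0/10: adherent.

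Three consecutive daily readings span 48 hours, so both examples stand even if the wording in section 10.7 requires the excess to last that long.

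**3. Early breaches diluted.** Take an experimental patient with 2 consecutive deviating days in the first 7: 2/7 = 29%. With 14 in-range days afterwards this becomes 2/21 = 9.5%, and the patient passes. At 20 days, 2/20 = 10% is not below 10%, so at least 21 daily values are needed. The example also requires that two consecutive daily readings count as a deviation. If three are required, dilution cannot rescue anyone at one value per day, because 3/30 = 10.0% still fails.

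**4. What this could do to the trial result.** 0.80 × 72 = 57.6, so at least 58 patients must pass (58/72 = 80.6%; 57/72 = 79.2%). If true adherence is 90%, the binomial probability of 58 or more is 0.995. If, as an assumption, 10% of adherent patients were wrongly failed, the observed rate would be 0.90 × 0.90 = 0.81 and the probability falls to 0.61. At 5% wrongly failed it is 0.91, and at 20% it is 0.07. The protocol gives no basis for choosing among these shares. They show sensitivity only.

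**The case against.** The strongest reply is that the protocol nowhere says exempt values are counted. Section 10.13 speaks of deviations from the explicit ventilation protocols, and those protocols include the releases in 8.1.2 and 8.2. On an ordinary reading a permitted value is not a deviation. The meaning of a major deviation and of a monitored value could also be set in an analysis plan or the Manual of Procedures.

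Part of this stands: the sections fail to exclude such values rather than require counting them. But section 10.7 spells out numerical thresholds, and an exempt value above 8 ml/kg meets them. Even if exempt values are dropped as deviations, nothing takes them out of the denominator. The conflict is between sections of the protocol itself, so it is more than detail left for later.

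Four stronger readings that a reader might infer are not supported:
- **That compliant patients do fail and non-compliant ones do pass.** Both can happen. No frequency can be taken from the document.
- **That an experimental patient off ECMO on low support at day 5 breaches a limit that a control patient in the same state does not.** Section 8.4 treats stopping ECMO before day 7 after a passed sweep-gas-off trial as consistent with the protocol. Section 6.1 contemplates conventional ventilation for some experimental patients, and section 8.3 sets common weaning for everyone not on ECMO. Such a patient may fall under 8.2 with its exemption. The document does not settle this.
- **That plateau pressure is released too after day 7.** Section 8.1.2 names driving pressure and tidal volume only. In the control arm's low-support state a plateau above 30 cm H₂O is unlikely anyway, so tidal volume is the realistic trigger.
- **That scoring both arms only to day 7 would put it right.** Section 8.2 sets no end day, so that window would discard control values whose limits still apply.

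**Conclusion.** The point holds as an inconsistency between the scoring rule and the treatment rules. Taken literally, sections 10.7 and 10.13 can score a patient who broke no limit in force as non-adherent, with 15% and 23% deviating values in the two examples against a 10% cut-off. These examples assume one value per day.

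The opposite error, early breaches hidden by later values, is the weaker part. It needs at least 21 daily values and the two-reading interpretation of the persistence wording.

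How often either error would occur is unknown, and the pass probabilities above rest on assumed shares. The pilot plans no formal inference, and no automatic stop is tied to the 80% figure. Even so, the criterion informs the decision on the definitive trial, so it should be settled before adherence is assessed.

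**What to change.** Reconcile sections 10.7 and 10.13 with 8.1.2 and 8.2:

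1. State that only values recorded while the protocol's own limit for that arm and variable is in force enter the numerator and the denominator of the 10% rule. For experimental tidal volume and driving pressure that means up to day 7. For control tidal volume and plateau pressure it means outside the low-support state of section 8.2.
2. State which limits apply to experimental patients who come off ECMO before day 7, and whether the experimental plateau-pressure limit continues after day 7.
3. Report all other values descriptively, and report adherence by arm.

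This changes scoring only and alters no clinical limit. The scoring rule takes about two sentences, and the two clarifications need a line each. Ventilation mode, PEEP, FiO₂ and tidal volume are already collected daily (section 6.2). The small cost is fewer scored values per patient, which makes the 10% rule coarser: with 10 or fewer values a single counted deviation fails the patient, since 1/10 is not below 10%.
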